## 6. Drugs/ Substances/ Devices

N/A

## 7. Study Statistics

Exploratory and descriptive analysis will be completed for all study variables. Variables will be examined for normality and examined with means and standard deviations or medians and interquartile ranges accordingly. Baseline characteristics comparing the two groups (waitlist vs. immediate intervention) will be assessed. Any differences between the groups will be adjusted for further analysis. The significance level will be set at 0.05. Sensitivity analyses will be conducted adjusting for variables on which the group differ and compared to the pattern of results in the main analyses.

### a. Primary outcome variable.

Generalized estimating equations (GEE) will be used to examine the difference between intervention and waitlist groups in change from baseline to 16 and to 32 weeks for QOL (primary outcome), considering affective well-being and physical health separately and together as an aggregate measure of QOL. Time, group and the group by time interaction will be included in the model. We will also calculate Hedges'  $g$  for differences in change over time between the groups in change in primary outcomes. Hedges'  $g$  is recommended over Cohen's  $d$  to correct of an upward bias in small sample sizes. The effect size associated with the variables will be compared to established clinically significant improvement reported in the literature, rather than placing emphasis on statistical significance.

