## Protocol

### 1. Abstract

Family caregivers who care for older adults living with multiple chronic conditions, including heart failure (HF), provide substantial cost savings to the US healthcare system. While caregiving can be meaningful and rewarding, extensive research also demonstrates high rates of chronic disease, fatigue and physiologic measures such as stress hormones among caregivers. Family caregivers are often left juggling their loved one's healthcare as well as their own. Unmet needs have been identified including increased stress, financial strain and social isolation, but interventions to address these needs in HF caregivers have had mixed results. Due to the limited impact of many caregiver interventions, experts have called for a greater understanding of the dynamic and contextual factors of family caregiving including resources, needs and social support with an increased focus on individualization of interventions for high-risk caregivers to improve outcomes. Following a mixed methods study to better understand these contextual factors and to address this gap between the evidence and uptake of proven strategies by caregivers, we have developed a resilience-promoting intervention to improve quality of life for family caregivers of individuals with multiple chronic conditions, including HF, Caregiver-Support. This home-based intervention is guided by effective strategies implemented by our co-investigator, [name], to support older adults in goal setting to promote healthy aging. Using these strategies, Caregiver-Support will help caregivers articulate statements of purpose in life, set goals to address fatigue and caregiver burden, provide instrumental support through a benefits check-up and promote identification and increased connection with the caregiver's social network.

The first phase of the study will be an open label pilot (N=5) followed by a single-masked, two-group, randomized trial (N=40) to test the feasibility and gauge an initial effect size of the intervention.

Participants will be visited by study staff in their homes for data collection and intervention visits.

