## 4. Study Procedures

**Figure 2: Flowchart of Study Design**

control groups are used to first provide an untreated comparison and second to allow wait-listed participants an opportunity to receive the intervention at a later date. This is especially appropriate given that very few services are currently offered to HF caregivers. To account for estimated 20% attrition we will recruit 53 participants.

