### **Johns Hopkins Bayview Clinic Recruitment:**

We will distribute a recruitment flyer in the heart failure clinic at the Johns Hopkins Bayview Medical Center. Caregivers that respond to the recruitment flyer will be screened for eligibility. If they are eligible, we will contact them by phone to explain study procedures. If interested in participating, we will schedule the caregiver's baseline interview within 10 days of initial contact. During the baseline interview the research assistant will re-explain the study, obtain written consent (if interview is in-person), or e-consent (if the interview is by phone or DoxyMe or Zoom video call).

**Overview of Study Design (Figure 2):** We propose an open label pilot (n=5) with a subsequent single-blind, two group randomized pilot trial to test the feasibility and gauge an initial effect size of the Caregiver-Support intervention to improve QOL. The immediate intervention group (n=20) will receive the intervention during weeks 0-16. The waitlist control group (n=20) will be provided written materials with community resources for caregivers during the first 16 weeks, then they will begin the intervention. Waitlist

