## **Open Label Phase:**

The first five participants will be enrolled into an open label pilot study, in which they will automatically receive the Caregiver-Support intervention. The participants will be interviewed after program completion to get feedback on the data collection instruments, intervention content including the number of visits and user-friendliness of intervention components (e.g. purpose in life activity), and satisfaction with the overall program process. This feedback will be used to modify the Caregiver-Support intervention for the waitlist control trial that will begin enrollment following the open label phase.

**Randomization:** Within 48 hours of the baseline interview, we will randomize using redcap randomization and communicate the assignment to participants by letter. At that same time, we will inform the nurse interventionist of the new participant. The intervention nurse will contact the participant within one week to schedule the first appointment. The waitlisted group will receive usual care for caregivers for the first 16 weeks, which is normally limited to inclusion in some clinical assessment and teaching during patient visits. Waitlisted participants will receive monthly study postcards to encourage retention. After 16 weeks, they will begin the intervention. The 32- week assessment will measure whether immediate intervention participants continue the strategies on their own and whether they continue to improve on the self-report scales and will measure improvement following the intervention for waitlisted participants.

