### c. Statistical plan including sample size justification and interim data analysis.

As a pilot study, the analyses will likely not have adequate power to detect significant differences. Therefore, effect sizes, rather than statistical significance will be examined for evidence of the effectiveness of the intervention. With a total sample size of 53 we will be able to estimate the effect size associated with the intervention. This effect size will be compared to the literature for similar interventions and used to estimate the needed sample size to a fully powered effectiveness trial. There will be no interim data analysis.

Understanding the factors that predict which intervention components are successfully implemented and for which participant subgroups will be critical for fine-tuning this multicomponent intervention for future proposals that will extend efficacy examinations and effect modification analyses. Acceptability of the intervention will be examined in multiple ways. We will examine percentages of people who stayed in each arm of the study and conduct numerous descriptive correlational analyses of the association between

the intervention compliance and other variables. These analyses will quantify intervention implementation by demographic and participant health variables. Analyses that utilize the post-randomization data (e.g. treatment compliance) will be evaluated in supplementary analyses. We will distinguish non-compliance with intervention from attrition or loss to follow-up, i.e. missing data. We will also use the participant satisfaction data to examine acceptability of the intervention.

d. Early stopping rules.

As this is a low-risk behavioral intervention pilot, we have not defined any early stopping rules.

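### GEE on about 40 caregivers with 20% attrition is planned without a working correlation, small-sample variance or missing-data method; under customary settings its 95% intervals would be about 5–7% too narrow

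*Combined protocol and SAP*

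**What the plan says.** For the primary outcome, section 7a states: "Generalized estimating equations (GEE) will be used to examine the difference between intervention and waitlist groups". On the mean model it adds: "Time, group and the group by time interaction will be included in the model". Section 7b applies a similar approach to fatigue, caregiver burden, cytokines (log-transformed if needed) and heart rate variability. Care-recipient outcomes are handled differently, by chi-square and t-tests.

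On size, the Abstract describes a "single-masked, two-group, randomized trial (N=40) to test the feasibility and gauge an initial effect size of the intervention", and the design overview in section 4 says: "The immediate intervention group (n=20) will receive the intervention during weeks 0-16", with the same number on the waitlist. Section 4 also says: "To account for estimated 20% attrition we will recruit 53 participants". Before randomisation starts, "The first five participants will be enrolled into an open label pilot study".

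On missing follow-up, the only statement is in section 7c: "We will distinguish non-compliance with intervention from attrition or loss to follow-up, i.e. missing data". The sensitivity analyses in the opening paragraph of section 7 concern baseline differences between groups, not dropout. That paragraph also sets the 0.05 significance level. Section 7a chooses Hedges' g to limit small-sample bias in the effect size. No matching provision is made for the GEE standard errors.

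**The concern.** Two gaps sit in the same analysis.

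The first is precision. The usual GEE sandwich variance is biased downward when there are few independent units, and a z or chi-square reference ignores the uncertainty in estimating it. With about 20 caregivers per arm, both push towards intervals that are too short.

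The second is dropout. Unweighted GEE is guaranteed in general only when dropout is completely at random. How far it departs from that in practice depends on the working correlation, which is unstated. Some difference in dropout between arms is plausible. One arm gets nurse visits from week 1 while the other gets usual care and monthly postcards for 16 weeks, and Table 1 itself suggests that instrumental support may help retention.

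The main product of this pilot is an effect estimate that section 7c will use to size a full trial. An interval that is too short overstates how well that estimate is known. A biased estimate would carry straight into the next sample size.

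**Working it through.** **Inputs from the protocol:** 40 randomised, 20 per arm (Abstract; section 4); 20% attrition and 53 recruited (section 4); 5 open-label participants (section 4); level 0.05 (section 7), taken as two-sided; mean model of time, group and their interaction (section 7a).

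**Assumptions not in the protocol:** normal outcome, SD 10, within-person correlation 0.6, 20% monotone dropout, no true effect.

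**Step 1: the plan's figure of 53.** No derivation is shown. 40 × 1.2 = 48, and 48 + 5 = 53, which matches exactly. Dividing instead gives 40 / 0.8 = 50, and 50 + 5 = 55. Section 7c nevertheless says: "With a total sample size of 53 we will be able to estimate the effect size associated with the intervention". The number available at follow-up therefore depends on the reading:
- 40 randomised: 40 × 0.8 = 32, or 16 per arm.
- 48 randomised: 48 × 0.8 = 38.4, about 19 per arm.
- 53 randomised: 53 × 0.8 = 42.4, about 21 per arm.

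The range of 16 to 24 per arm used below covers these.

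**Step 2: closed form, complete data.** In the saturated group-by-time model the week-16 contrast is a difference in mean change. With n per arm, sandwich SE = usual SE × √((n−1)/n).
- Width ratio = 1.960 × √((n−1)/n) / t(0.975; 2n−2)
- Coverage = P(|T| < 1.960 × √((n−1)/n)), with T on 2n−2 degrees of freedom

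| n per arm | 1.960 × √((n−1)/n) | t critical value | width ratio | coverage | type I error |
|---|---|---|---|---|---|
| 16 | 1.898 | 2.042 | 0.929 | 93.3% | 6.7% |
| 20 | 1.910 | 2.024 | 0.944 | 93.6% | 6.4% |
| 24 | 1.919 | 2.013 | 0.953 | 93.9% | 6.1% |

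For scale, at 20 per arm the correct half-width for a standardised difference in change is 2.024 × √(2/20) = 0.640. The uncorrected one is 0.640 × 0.944 = 0.604.

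**Step 3: simulation, 20% dropout completely at random, week-16 contrast.** 3,000 runs at 20 per arm and 2,000 at 24.

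| Method | 20/arm: coverage, half-width | 24/arm: coverage, half-width |
|---|---|---|
| GEE exchangeable, sandwich, z | 93.1%, 5.86 | 93.8%, 5.39 |
| GEE independence, sandwich, z | 93.4%, 6.17 | 93.8%, 5.67 |
| GEE exchangeable, Mancl-DeRouen, t | 95.1%, 6.45 | 95.6%, 5.83 |
| GEE independence, Mancl-DeRouen, t | 95.8%, 6.77 | 95.6%, 6.13 |
| REML mixed model, unstructured, Kenward-Roger | 94.5%, 6.30 | 95.0%, 5.72 |

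A separate simulation at 20 per arm, with correlation 0.5 to 0.7, gave a type I error of about 6.0% with complete data and 6.5–6.7% with 20% random attrition. Mancl-DeRouen with t gave 4.1–4.4%, so it is slightly conservative.

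**Step 4: simulation, informative dropout, 20 per arm, 1,500 runs each.** Entries are bias in points on SD 10 and 95% coverage. Both GEE columns use sandwich and z.

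| Dropout depends on | GEE independence | GEE exchangeable | Mixed model |
|---|---|---|---|
| baseline score, alike in both arms | 0.0, 93.0% | 0.0, 93.1% | 0.0, 94.9% |
| baseline score, opposite by arm | 2.2, 89.8% | 0.2, 92.7% | 0.1, 94.4% |
| week-16 score, opposite by arm (week-32 contrast) | 2.1, 88.4% | 0.0, 92.8% | −0.05, 93.5% |
| same, true correlation AR(1) | 2.3, 91.3% | 0.4, 94.4% | 0.2, 95.9% |
| unseen week-16 score, opposite by arm | 3.5, 80.2% | 2.3, 86.5% | 2.4, 88.9% |

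Monte Carlo error of coverage, √(p(1−p)/runs), is about 0.4 to 1.0 percentage points.

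**Step 5: what 0.2 SD would do to the next trial.** Suppose the true effect were 0.5 SD (an assumption). Read as 0.7, it gives (0.5/0.7)² = 0.51 of the needed sample. Read as 0.3, it gives (0.5/0.3)² = 2.78 times it.

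**The case against.** The strongest reply is that the plan never states the variance method being criticised. That is correct: the sandwich variance and z reference are inferred from customary practice. A reader might infer that the plan as written breaches its own 0.05 level, but the documents support only that the estimator is unspecified and that the customary choice would do so.

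Sections 7a and 7c also put effect size ahead of significance and admit low power, and a standard error that is too small does not change a point estimate. This stands too, and it makes the precision issue modest. It does not remove it. An effect size meant to plan a trial needs an honest interval, and a significance level is still set.

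Three stronger readings are tempting and not supported:
- **That attrition will bias the GEE estimate.** No passage indicates that dropout will depend on scores in opposite directions by arm. The 0.2 SD figure also needs an independence working correlation. It nearly vanishes with an exchangeable one.
- **That GEE must be replaced because a mixed model avoids both problems.** Corrected GEE restores coverage. A mixed model only relaxes the assumption to missing at random, and under not-at-random dropout its bias was 2.4 points against 2.3 for exchangeable GEE.
- **That every secondary outcome is affected.** The care-recipient outcomes do not use GEE.

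Finally, 40 may be the intended number of completers, so that removing a further 20% counts attrition twice. The 20- and 24-per-arm rows cover that reading, and the direction is unchanged.

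**Conclusion.** The concern holds as a gap in specification with a modest, calculable effect. Under customary sandwich/z inference, 95% intervals for the outcomes analysed by GEE would cover about 93–94% and be about 5–7% too narrow. Type I error would be about 6.0–6.7%. The closed form for this rests only on complete data, a normal outcome and 16 to 24 caregivers per arm.

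The dropout part is conditional. Bias of about 0.2 SD requires both an independence working correlation and arm-opposed dependence on earlier scores. Since the plan fixes neither the working correlation nor a missing-data assumption, it does not exclude that result, but nor does it predict it. The gap should be closed before the data are analysed. It does not call the design into question.

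**What to change.** In sections 7a and 7b, for quality of life, fatigue, burden, cytokines and heart rate variability, specify one of two options:
- **Keep GEE**, with an exchangeable or unstructured working correlation, the Mancl-DeRouen variance and a t reference. Its protection under missing-at-random dropout relies on the working correlation being close to the truth.
- **Use a REML mixed model** with unstructured covariance and Kenward-Roger degrees of freedom.

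Under either option:
- Derive the effect size and its confidence interval from the fitted model. The plan does not say whether Hedges' g comes from the model or from observed change scores, and the latter would use completers only.
- State the missing-at-random assumption.
- Add one sensitivity analysis under not-at-random dropout, because neither method protects against it.
- Say whether 53 includes the five open-label participants, and how many are randomised.

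The cost is analysis wording and a little more analysis work, with no new data or visits. Intervals become slightly wider. In the closed form the increase is about 5–8% (1/0.953 = 1.049; 1/0.929 = 1.076). In the simulation, against exchangeable GEE with sandwich and z, it is about 6–8% for the mixed model (5.72/5.39 = 1.061; 6.30/5.86 = 1.075) and 8–10% for Mancl-DeRouen with t (5.83/5.39 = 1.082; 6.45/5.86 = 1.101).

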Participants will be randomized to receive either the immediate intervention group or the waitlist control group. In the waitlist control group, participants will receive usual care for the first 16 weeks (which is limited to printed materials provided in the clinic) and then begin the intervention. The intervention will consist of 5 in-home sessions with a nurse interventionist. Each participant will receive each intervention component but interventionists will systematically tailor content to the participants' goals based on protocols. All participants will be reassessed at 16 weeks and 32 weeks by a research assistant (RA) masked to treatment condition. The primary outcome will be improvement in quality of life between baseline and 16 weeks. Other endpoints include group differences in fatigue, caregiver burden, self-reported and physiological measures of resilience up through 32 weeks after the intervention. We will also examine the acceptability of the intervention using intervention compliance and participant satisfaction data.

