### b. Secondary outcome variables.

Generalized estimating equations (GEE) will be used to examine the difference between intervention and waitlist groups in change from baseline to 16 and to 32 weeks for fatigue and caregiver burden (secondary outcomes) using a similar approach (as described for primary outcome). We will use a similar approach to analyze cytokines and HRV. Given previous research in adults with chronic disease, we assume that the cytokine data will require log transformation to approach normality.

We compare differences in care recipient palliative care utilization, hospice enrollment, hospital admission, and mortality 6 months after caregiver completion of the intervention between intervention and control groups. We will use chi-square test to determine differences in rates of these outcomes and t-tests to compare average time to event between groups.

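### The primary GEE estimates the week-16 QOL effect as a raw difference in mean change; prespecified baseline adjustment would usually give a more precise effect size from data already collected

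*Combined protocol and SAP*

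**What the plan says.** The Abstract (section 1) defines the endpoint: "The primary outcome will be improvement in quality of life between baseline and 16 weeks".

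Section 7.a analyses QOL by GEE, taking affective well-being and physical health separately and as an aggregate, over baseline, week 16 and week 32. On the model terms it says: "Time, group and the group by time interaction will be included in the model". It adds Hedges' g "for differences in change over time between the groups in change in primary outcomes". Baseline QOL therefore enters only as the first repeated outcome. It is not a covariate, and the arms are not given a common baseline mean. The coding of time, the working correlation and the SD that divides g are not stated.

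The opening of section 7 has two sentences on adjustment. One reads "Any differences between the groups will be adjusted for further analysis"; the other reads "Sensitivity analyses will be conducted adjusting for variables on which the group differ and compared to the pattern of results in the main analyses".

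Section 7.b uses a similar approach for fatigue and caregiver burden, and says of the physiological measures: "We will use a similar approach to analyze cytokines and HRV".

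Section 7.c puts effect sizes ahead of significance. The estimate is to be compared with the literature and "used to estimate the needed sample size to a fully powered effectiveness trial".

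**The concern.** A group-by-time model with a free baseline mean in each arm subtracts the whole baseline difference between arms, whatever the correlation between baseline and follow-up. Under randomisation that difference is chance. When the regression of week 16 on baseline has a slope below 1, subtracting all of it adds noise that a fitted slope would remove.

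The estimate concerned is the one the pilot passes on to the design of the next trial. With 20 per arm it will be imprecise under any analysis, so precision available from a score already collected is worth having. At stake is the width of the interval around the effect size, not the validity of the estimate.

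**Working it through.** **The plan's own figures.** Section 4 says "To account for estimated 20% attrition we will recruit 53 participants". The randomised comparison is 20 + 20 = 40. Then 40 × 1.20 = 48, and adding the 5 open-label participants gives 53. (Dividing instead gives 40/0.80 + 5 = 55.) Counting the open-label five is an assumption, and nothing below depends on it. No SD, correlation or power is stated, so no planned precision can be reproduced. I use n = 20 per arm.

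**Step 1: what the stated model estimates.** GEE was fitted to simulated complete data, with three visits, categorical time and 20 per arm. The group by week-16 coefficient equalled the raw difference in mean change under independence, exchangeable and unstructured working correlation. In one data set both were 0.77358, while ANCOVA on the same data gave 0.43134. With linear time or missing week-16 data the equality no longer holds exactly.

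**Step 2: does a simple covariate help?** In a second data set the coefficient was 0.25134. Adding baseline QOL, or another baseline variable, as a main effect left it at 0.25134. Adding baseline by time moved it to 0.13828, exactly the ANCOVA estimate.

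**Step 3: variance.** Set the baseline SD to 1, the week-16 SD to k and the baseline to week-16 correlation to r. Each variance below is multiplied by 2/n.

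- Change: 1 + k² − 2rk
- Baseline-adjusted: k²(1 − r²) × (1 + 1/36), where 36 = 2n − 4 and the last factor is the cost of estimating the slope

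The documents give neither r nor k, so both are assumed over a range.

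| k | r | Change | Adjusted | Ratio | Variance reduction |
|---|---|---|---|---|---|
| 1 | 0.4 | 1.200 | 0.863 | 0.719 | 28% |
| 1 | 0.6 | 0.800 | 0.658 | 0.822 | 18% |
| 1 | 0.8 | 0.400 | 0.370 | 0.925 | 7.5% |
| 0.8 | 0.4 | 1.000 | 0.553 | 0.553 | 45% |
| 0.8 | 0.6 | 0.680 | 0.421 | 0.619 | 38% |
| 0.8 | 0.8 | 0.360 | 0.237 | 0.658 | 34% |
| 1.25 | 0.4 | 1.563 | 1.349 | 0.863 | 14% |
| 1.25 | 0.6 | 1.063 | 1.028 | 0.967 | 3% |
| 1.25 | 0.8 | 0.563 | 0.578 | 1.028 | −3% |

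The last row is explained by the slope, which is rk = 0.8 × 1.25 = 1. Change is then already the best linear adjustment, and estimating the slope only costs precision.

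**Step 4: interval width, k = 1.** In baseline SDs, the 95% half-width for change is t(38) × √(4(1 − r)/20) = 0.701, 0.573 and 0.405 at r = 0.4, 0.6 and 0.8. Adjusted, it is t(37) × √(2(1 − r²)/20 × 37/36) = 0.595, 0.520 and 0.390.

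**Step 5: bias.** In 10,000 simulated trials at each of r = 0.3, 0.5 and 0.7 with a true effect of 0.40, the mean of both estimators lay between 0.39 and 0.41. The variance ratios were 0.66, 0.78 and 0.88, in line with the formula.

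**Step 6: attrition, k = 1.** Suppose 24 per arm are randomised and 4 per arm miss both follow-ups completely at random. With exchangeable correlation r known, the stated model has variance 2[(1 − r²)/20 + (1 − r)²/24] = 0.1140, 0.0773 and 0.0393. Baseline adjustment on the 20 followed up per arm gives 0.0863, 0.0658 and 0.0370, a reduction of about 24%, 15% and 6%. The gain shrinks but remains.

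**The case against.** The strongest reply is that nothing here is wrong. Endpoint, model and effect size all concern change, and under randomisation the change estimate is valid. That stands. A reader might infer that the planned estimate is biased or that the model must be rejected; the documents do not support this, and the simulations show no bias.

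Second, the gain may be small. At r = 0.6 with equal SDs the half-width falls only from 0.57 to 0.52, and either interval is wide for sizing a trial. With a larger week-16 SD the gain can vanish or slightly reverse. This also stands, and without r or the SDs no single figure can be claimed.

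Third, section 7 already promises adjustment. It gives no form, and a baseline-by-time term would deliver the full gain, so it would be too strong to call that adjustment useless. But it is triggered by observed differences, and it is described both as adjustment for later analyses and as a sensitivity analysis. In its simplest form, a main effect, it does nothing for the week-16 interaction on complete data. It cannot be relied on.

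Fourth, the effect size is not the pilot's only purpose. Aim 1 pairs it with feasibility, and section 7.c also covers acceptability. That is fair; the point concerns the effect-size part alone.

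Fifth, the intervals in Step 4 are classical t intervals, not GEE intervals. In 400 simulated trials at r = 0.6 the usual robust standard error gave a mean half-width of 0.53 for the stated model, with coverage near 92%. The variance comparison is unaffected, but a GEE with 40 participants needs a small-sample correction.

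**Conclusion.** The point holds as one of efficiency and should be acted on. With categorical time and complete data, the stated model gives the raw difference in mean change at week 16, and the plan does not reliably recover the precision that the baseline score offers. With 20 per arm and r from 0.4 to 0.8, the variance reduction runs from 28% to 7.5% with equal SDs, from 45% to 34% if the week-16 SD is 0.8 times baseline, and from 14% to −3% if it is 1.25 times. Both r and the SD ratio are assumptions. Confidence is medium, because the documents fix neither.

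The unstated SD for g and the unstated time coding are gaps to fill, but they do not carry the point. A reader might infer that g on change is wrong. It is not: g over the change SD is usable for a later trial analysed by change, provided it is labelled. With equal SDs it differs from g over the baseline SD by the factor 1/√(2(1 − r)), which is 0.91 at r = 0.4 and 1.58 at r = 0.8.

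**What to change.** For each QOL score (affective, physical, aggregate), fatigue and burden, prespecify one model whatever the observed imbalance:

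- GEE with weeks 16 and 32 as outcomes; categorical time, group and group by time; the baseline value of the same score as covariate, with baseline by time.
- A small-sample-corrected robust standard error, with the week-16 contrast as primary.
- Hedges' g from that adjusted difference over the pooled baseline SD, with a 95% CI.
- The change SD and the baseline to week-16 correlation reported as well, so that the next trial can be sized under either analysis.
- Adjustment for observed imbalance kept as a sensitivity analysis only, with the opening of section 7 reworded to say so.

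With complete data the week-16 contrast from this model is the ANCOVA estimate, so the Step 3 figures apply to it. Cytokines and HRV need their own specification: the data-collection section defers those measurements under COVID-19 restrictions, so some baseline values may be absent.

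The cost is a rewrite of the model text in section 7, with standard software and no added participant burden. The model spends one or two degrees of freedom and drops anyone without a baseline value. There is little or no gain if r is high or the week-16 SD is clearly larger than at baseline.
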